5.2.1.3 Urinalysis

Urinalysis assessments will include the following: pH, specific gravity, glucose (urine glucose will be blinded throughout the study), blood, ketones, protein, and microscopic analysis (or other routine urinalysis as approved by the Sponsor).

5.2.1.4 Other Clinical Laboratory Evaluations

Fasting lipid panel

Fasting serum lipids (total-cholesterol, LDL-cholesterol, HDL-cholesterol, non-HDL cholesterol, and triglycerides) will be assessed at Screening (Visit 1), Baseline (Visit 3), Week 28 (Visit 12), Week 52 (Visit 15), and Week 104 (Visit 19).

Fasting glucagon

Fasting plasma glucagon will be collected according to the schedule presented in the Study Plan ([Table 1](#) and [Table 2](#)).

Calcitonin

Blood samples will be drawn for measurement of calcitonin concentrations according to the schedules presented in the Study Plan ([Table 1](#) and [Table 2](#)).

If an elevation of calcitonin is noted and deemed of clinical concern:

- The investigator should assess for factors that could be impacting calcitonin concentrations (ie, concomitant medications) and consider stopping them prior to rechecking calcitonin concentrations.

- If calcitonin concentrations remain elevated upon recheck, the patient should be referred to their healthcare provider for appropriate follow-up.
- Any subsequent testing and interpretation of results should be provided to the study site personnel.
- The investigator should discuss patient continuation in the study with the medical monitor.

The investigator should make an assessment of the available results with regard to clinically relevant abnormalities. The laboratory results should be signed and dated and retained at center as source data for laboratory variables. For information on how AEs based on laboratory tests should be recorded and reported, see Section 6.3.

Thyroid Stimulating Hormone (TSH)

Blood samples will be collected for the measurement of thyroid stimulating hormone (TSH) at Screening, as presented in the Study Plan (Table 1 and Table 2). Abnormal TSH values will be further evaluated by free T4. Patients with abnormal free T4 values will be excluded.

Pregnancy Testing

All female patients, regardless of childbearing status (unless patient has had a hysterectomy), will provide blood or urine samples for pregnancy tests according to the schedules presented in the Study Plan (Table 1 and Table 2). The first dose of study medication or any other in-clinic dose of study medication will not be administered until a negative result is obtained.

Antibodies to Exenatide

Blood samples will be collected for the measurement of antibodies to exenatide according to the schedules presented in the Study Plan (Table 1 and Table 2).

Anti-exenatide antibody samples will be retained at the AZ Biobank or an AZ approved storage facility for up to a maximum of 15 years after the study completion date or according to local legislation. Samples may be destroyed prior to this timeframe if the patient has withdrawn consent or the samples are no longer required. The anti-exenatide antibody samples may be disposed of or destroyed and anonymized by pooling.

Additional analyses for anti-exenatide antibodies may be conducted. In addition, analyses may also be conducted on the anonymized, pooled anti-exenatide antibody samples to further evaluate and validate the analytical method. Any results from such analyses may be reported separately from the clinical study report (CSR).

Biological Samples for Future Research (Samples to Be Archived)

Up to 10 additional blood samples (approximately 5 to 6 mL each) will be collected at up to 5 different time points (ie, up to 2 samples at each time point) according to the schedule

presented in the Study Plan ([Table 1](#) and [Table 2](#)) for potential future measurement of other analytes, if indicated upon review of the data.

Biological samples for future research will be retained at the AZ Biobank or an AZ approved storage facility for a maximum of 15 years after the study completion date or according to local legislation. Samples may be destroyed prior to this timeframe if the patient has withdrawn consent.

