4. STUDY PLAN AND TIMING OF PROCEDURES

[Table 1](#) (Study Plan [Part 1] – 28-week Treatment Period) and [Table 2](#) (Study Plan [Part 2] – Extension Period 1, Extension Period 2, and Follow-up) present the schedule of assessments for this study.

Table 1 Study Plan (Part 1) – 28-week Treatment Period

Evaluation	Screening Visit	Lead-in Visit	28-week Treatment Period									End of Treatment Period	Treatment Period: Early Termination	Treatment Period: Rescue
			3	4	5	6	7	8	9	10	11			
Visit Number	1	2	3	4	5	6	7	8	9	10	11	12	ET - TX	Rescue - TX
Week	-2	-1	0	1	2	4	8	12	16	20	24	28		
Relative to Randomization (days)	-14	-7	R	7	14	28	56	84	112	140	168	196		
Visit Window (days)	0	(±7)	(±3)	(±3)	(±3)	(±3)	(±3)	(±3)	(±3)	(±3)	(±3)	(±3)		
Informed Consent	X													
Medical History	X													
Verify Inclusion/Exclusion Criteria	X		X											
Verify patient has fasted 8 hours	X	X	X	X	X	X	X	X	X	X	X	X	X	X
Contact IVRS	X	X	X	X	X	X	X	X	X	X	X	X	X	X
Randomization			X											
Complete Physical Examination	X											X	X	X
Brief Physical Examination		X	X	X	X	X	X	X	X	X	X			
Body weight	X		X	X	X	X	X	X	X	X	X	X	X	X
Waist Circumference			X									X	X	X
Height	X													
Body Mass Index	X		X									X	X	X
Vital signs (seated BP and HR)	X	X	X	X	X	X	X	X	X	X	X	X	X	X
12-lead ECG	X											X	X	X
AEs/potential CV event triggers		X	X	X	X	X	X	X	X	X	X	X	X	X
Concomitant medication review	X	X	X	X	X	X	X	X	X	X	X	X	X	X
Assess hypoglycemia episodes		X	X	X	X	X	X	X	X	X	X	X	X	X
Serum βhCG Test	X											X	X	X
Urine βhCG Test		X	X	X	X	X	X	X	X	X	X			
Urine glucose/creatinine ratio			X	X	X	X	X	X	X	X	X	X	X	X
Chemistry, hematology, urinalysis	X		X	X	X	X	X	X	X	X	X	X	X	X
Serum calcitonin	X											X	X	X
HbA1c	X	X	X			X	X	X	X	X	X	X	X	X
Fasting plasma glucose	X	X	X ^b	X	X	X	X	X	X	X	X	X ^b	X ^b	X ^b
Fasting insulin			X ^b									X ^b	X ^b	X ^b

Evaluation	Screening Visit	Lead-in Visit	28-week Treatment Period									End of Treatment Period	Treatment Period: Early Termination	Treatment Period: Rescue
			3	4	5	6	7	8	9	10	11			
Visit Number	1	2	3	4	5	6	7	8	9	10	11	12	ET - TX	Rescue - TX
Week	-2	-1	0	1	2	4	8	12	16	20	24	28		
Relative to Randomization (days)	-14	-7	R	7	14	28	56	84	112	140	168	196		
Visit Window (days)	0	(±7)	(±3)	(±3)	(±3)	(±3)	(±3)	(±3)	(±3)	(±3)	(±3)	(±3)		
Fasting C-peptide			X ^b									X ^b	X ^b	X ^b
Fasting glucagon			X ^b									X ^b	X ^b	X ^b
Serum Creatinine (Screening), creatinine clearance (Cockcroft-gault)	X		X	X	X	X	X	X	X	X	X	X	X	X

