Prior to this visit, patients are to have fasted overnight (at least 8 hours), and to have abstained from strenuous exercise, alcohol, tobacco, and caffeine for 24 hours. Patients should delay administering the morning dose of metformin and study medication on the morning of the visit and bring OAD medication and study medication to the study-site visit.

The following procedures will be conducted:

- IVRS will be contacted to register an End of Treatment Period Visit or Early Termination visit; the IVRS will not be contacted for a Rescue visit.
- AEs, potential CV event triggers (Section [6.8.1](#)), and concomitant medications will be reviewed.
- A complete physical exam will be conducted (refer to Section [5.2.2](#)).
- Vital signs (sitting systolic and diastolic BP and HR) will be assessed.
- 12-lead ECG will be performed **prior to administration of study medication**.
- Body weight will be measured.
- BMI will be calculated.
- Waist circumference will be measured.
- Urine will be collected for the following assessments (to be collected right before time 0 of the meal tolerance test):
 - Urinalysis
 - Urine glucose/creatinine ratio.

- Meal tolerance test will be performed (refer to Section 5.1.6). (For patients who receive rescue treatment, the MTT should be performed before the rescue treatment is initiated. Also, for patients who prematurely and permanently discontinue study medication, the MTT should be performed before study medication is discontinued. After rescue therapy is initiated or study medication is discontinued, no further MTTs are required.)
- Blood samples will be collected after **administration of dapagliflozin** for the following assessments:
 - Serum pregnancy test (β hCG) for all female patients, unless patient has had a hysterectomy
 - Chemistry and hematology
 - Serum calcitonin
 - HbA1c
 - Fasting plasma glucose (need for rescue will be evaluated; part of meal tolerance test)
 - Fasting serum lipid concentrations (total cholesterol, LDL cholesterol, HDL cholesterol, non-HDL cholesterol, and triglycerides)
 - Fasting glucagon
 - Serum creatinine (calculated creatinine clearance; Cockcroft-Gault formula)
 - Fasting C-peptide (part of meal tolerance test)
 - Fasting insulin (part of meal tolerance test)
 - Serum antibodies to exenatide
 - Plasma exenatide and dapagliflozin. Samples for plasma dapagliflozin will be drawn 1 hour after administration of study medication as part of the meal tolerance test (refer to Section 5.1.6).

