1	Give dapagliflozin/placebo (and exenatide/placebo, if applicable) 1 hour BEFORE drawing the blood sample.	-60 minutes	-55 minutes
2	Collect urine for urinalysis.	-15 minutes	0 minutes
3	Draw the Time 0 blood sample 60 minutes AFTER administration of dapagliflozin/placebo. Samples should be drawn for glucose, insulin, C-peptide, glucagon, plasma dapagliflozin/placebo, and other laboratory tests due at the visit.	0 minutes	5 minutes
4	Administer the liquid meal supplement, starting immediately after the Time 0 blood samples are drawn. Liquid meal should be consumed over 10 minutes.	5 minutes	15 minutes
5	Draw specimens for post-liquid meal glucose, C-peptide, glucagon, and insulin at 120 minutes after Time 0 (Step 3).	120 minutes	125 minutes

At Week 52 (Visit 15), Week 104 (Visit 19), or Early Termination or Rescue, patients should delay administering oral study medication (dapagliflozin/placebo) on the morning of the visit and bring it to the study site visit. Dapagliflozin/placebo is given BEFORE administration of the liquid meal supplement. Exenatide/placebo is taken by the patient at the usual weekly scheduled time prior to the visit (or can be taken at the site if the patient is due for a dose at the time of the visit). Metformin should be taken by the subject at the next meal following completion of the MTT. The MTT at Week 52 (Visit 15)/Week 104 (Visit 19)/Early Termination/Rescue will only be done on patients who have not received rescue medication.

Please follow the steps below for MTT at Visit 15, Visit 19, or Early Termination or Rescue:

Step	Description	Starting Time Point	Ending Time Point
1	Give dapagliflozin/placebo (and exenatide/placebo, if applicable) 1 hour BEFORE drawing the blood sample.	-60 minutes	-55 minutes
2	Collect urine for urinalysis.	-15 minutes	0 minutes
3	Draw the Time 0 blood sample 60 minutes AFTER administration of dapagliflozin/placebo. Samples should be drawn for glucose, insulin, C-peptide, glucagon, and other laboratory tests due at the visit.	0 minutes	5 minutes
4	Administer the liquid meal supplement, starting immediately after the Time 0 blood samples are drawn. Liquid meal should be consumed over 10 minutes.	5 minutes	15 minutes
5	Draw specimens for post-liquid meal glucose, C-peptide, glucagon, and insulin at 120 minutes after Time 0 (step 3).	120 minutes	125 minutes

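### At Visits 12, 15 and 19, Early Termination and Rescue, the only scheduled pregnancy test is drawn after the in-clinic dose that Section 5.2.1.4 forbids until the test is negative

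*Protocol*

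**What the plan says.** **The rule.** Section 5.2.1.4 (Pregnancy Testing) covers every female patient who has not had a hysterectomy, whatever her childbearing status. These patients "will provide blood or urine samples for pregnancy tests according to the schedules presented in the Study Plan", and the first dose or "any other in-clinic dose of study medication will not be administered until a negative result is obtained".

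**The schedule.** In Table 1 the row "Urine βhCG Test" is marked at Visits 2 to 11 and is blank at Visit 12, Early Termination and Rescue. The row "Serum βhCG Test" is marked at Visit 1, Visit 12, Early Termination and Rescue. In Table 2 the urine row is marked at Visits 13, 14, 16, 17 and 18 only.

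**The visit procedures.** Section 4.2.2 (Visit 12, or Early Termination or Rescue in the treatment period) says: "Blood samples will be collected after administration of dapagliflozin for the following assessments". The first item in that list is "Serum pregnancy test (β hCG) for all female patients, unless patient has had a hysterectomy". The urine list in the same section holds only urinalysis and the glucose/creatinine ratio. Section 4.5 (Visits 15 and 19, or Early Termination or Rescue in the extensions) has the same arrangement.

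**The meal-test steps.** For these visits, step 1 in Section 5.1.6 is "Give dapagliflozin/placebo (and exenatide/placebo, if applicable) 1 hour BEFORE drawing the blood sample". The Time 0 draw, which includes the other laboratory tests due at the visit, is step 3.

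**The concern.** A rule that makes dosing conditional on a test result works only if the test can come first. At these visits the written order is dose, then sample, so the result that should permit the dose does not exist when the dose is given.

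The protocol treats fetal exposure as a matter of unknown risk (Section 1.2, Pregnancy or breastfeeding) and requires study medication to stop at once in pregnancy (Section 6.6.1). The pre-dose test is one of its safeguards. If sites follow the visit steps, each affected visit is a deviation from that safeguard, caused by the protocol itself. If sites follow the safeguard, they must rearrange the meal-test visit in a way the protocol does not describe, and different sites may do so differently.

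**Working it through.** The plan gives no figure to reproduce here. The check sets the passages side by side on one clock.

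**Visits 12, 15 and 19, Early Termination and Rescue (Section 5.1.6 step tables)**

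| Event | Time |
|---|---|
| Dapagliflozin/placebo, plus the injection if due | -60 to -55 min |
| Urine collected (urinalysis; no pregnancy test listed) | -15 to 0 min |
| Time 0 blood, including other tests due (serum pregnancy test) | 0 to 5 min |
| Liquid meal | 5 to 15 min |
| Post-meal blood | 120 to 125 min |

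Dose to pregnancy sample: 0 - (-60) = 60 minutes in the wrong direction. Even an instantaneous result would arrive an hour too late.

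**Visit 3 (Sections 4.1.4 and 5.1.6)**

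| Event | Time |
|---|---|
| Urine, including the pregnancy test | right before 0 min |
| Study medication | 125 to 130 min |

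Here the sample precedes the dose by about 125 minutes, so there is no conflict.

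**Other treatment and extension visits.** At Visits 4 to 11, 13, 14 and 16 to 18 a urine pregnancy test is scheduled at the visit, so the rule can be met there.

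**Is the in-clinic dose optional?** No. Sections 4.2.2, 4.5 and 5.1.6 tell patients to hold the morning oral dose and bring it, and Section 5.1.6 has it given before the liquid meal. Every arm takes a tablet, active or placebo, so the step applies to all three arms.

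**Who is affected?** Women without a hysterectomy who are still on study medication. Women already off study medication who return for the Week 28, 52 or 104 assessments take no dose, so the rule does not bite. Women already rescued need no further meal test. They stay on study medication, however, and Sections 4.2.2 and 4.5 still list their blood as taken after dapagliflozin.

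**A point not relied on.** In the text available, one Table 2 serum entry appears under the Week 48 telephone contact rather than Week 52. This may come from reading the table out of the PDF. Section 4.5 places the serum test at Visit 15 in any case.

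**The case against.** **An earlier negative result might satisfy the rule.** Section 5.2.1.4 does not say in terms that the result must come from the same visit. The preceding scheduled test would then be Visit 11 for Visit 12 (28 - 24 = 4 weeks old), Visit 14 for Visit 15 (52 - 44 = 8 weeks) and Visit 18 for Visit 19 (104 - 91 = 13 weeks). This reading is possible but strained. The protocol nowhere provides for carrying a result forward, and Visits 3 to 11 each schedule a same-visit urine test. A negative test at Visit 1 is already required for entry, so if an old result sufficed, extending the rule to any other in-clinic dose would add little.

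**The added exposure is small.** Patients take tablets daily and injections weekly at home without a test before each dose. The tablet at issue is one of about 28 x 7 = 196 up to Week 28. This stands, and it limits the clinical weight of the point. It does not remove the contradiction: the protocol chose to apply a stricter rule to in-clinic doses and then made it impossible to follow.

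**A stronger reading to resist.** A reader might infer that following Section 5.2.1.4 would cost the Week 28 2-hour postprandial glucose values and the 1-hour dapagliflozin samples in women, with a matching loss of precision on that secondary endpoint. The documents do not support this. The meal-test steps are timed relative to one another from the dose, so a later dose can move the whole sequence together and leave the intervals intact. The protocol gives neither the expected share of women nor the turnaround time of the pregnancy tests, so no loss can be estimated. All three blinded arms follow the same steps, so nothing in the design makes any loss differ by arm.

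**Conclusion.** The point holds as an internal contradiction, confined to Visits 12, 15 and 19 and to Early Termination and Rescue. At these visits the only scheduled pregnancy sample follows the mandatory in-clinic dose by 60 minutes, against a rule that bars the dose until a negative result. A woman without a hysterectomy who stays on study medication to Week 104 meets the conflict at three scheduled visits. The number of such women cannot be taken from the protocol.

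The conclusion assumes the natural reading of Section 5.2.1.4, that the negative result belongs to the visit at which the dose is given. On the looser reading the text is ambiguous rather than contradictory, and it still needs correction.

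The matter concerns patient safety procedure and protocol compliance. The primary endpoint, sample size, power and alpha are unaffected.

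**What to change.** Reconcile Section 5.2.1.4 with Sections 4.2.2, 4.5 and 5.1.6 and with the serum and urine pregnancy-test rows of Tables 1 and 2. For Visits 12, 15 and 19, Early Termination and Rescue, state once the order of pregnancy result, in-clinic dose and Time 0 sample. Use the same order in every section, and make sure it can be carried out within the visit. The text should also say whether the required result must come from that visit.

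Which clinical rule applies, and which test serves it, is for the sponsor to decide. This review does not propose one.

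The cost is a wording change in four sections and a check of two table rows, made through the protocol's own amendment process (Section 10.5). No analysis, sample size or endpoint definition needs to change.

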5.2.2 Physical examination

A complete physical examination should be performed according to the schedules presented in the Study Plan ([Table 1](#) and [Table 2](#)). The complete physical examination includes the following: general appearance including skin inspection (including injection site), lymph nodes, thyroid, musculoskeletal/extremities, cardiovascular, lungs, abdomen, and reflexes. Baseline physical examination data are collected at Visit 1, and new findings at the following physical examinations are recorded as change from baseline.

A brief physical examination should be conducted according to the schedules presented in the Study Plan ([Table 1](#) and [Table 2](#)). A brief physical examination includes the following: skin (including injection site), extremities, cardiovascular, lungs, and abdomen. Baseline data is collected at Day 0 during the full physical examination, and new findings at the following physical examinations are recorded as change from baseline.

Clinically significant abnormalities in physical examination findings at study termination must be followed up by the investigator and evaluated with additional tests if necessary, until the underlying cause is diagnosed or resolution occurs. As appropriate, the diagnosis and resolution date physical examination abnormalities must be reported as AEs.

Refer to Section [6.1](#) for reporting AEs.

5.2.3 ECG

A 12-lead ECG will be performed at Visit 1 (Screening), unless the patient has had a satisfactory ECG result in the past 6 months. Additional 12-lead ECGs will be performed according to the schedules presented in the Study Plan ([Table 1](#) and [Table 2](#)).

Standard 12-lead ECGs will be performed after approximately 5 minutes of quiet rest with the patient in a supine position. If the ECG must be performed with the patient in another position (sitting, standing, etc), the investigator should record the alternate position. The investigator should date and sign the ECG tracing and record the clinical significance of any abnormal result on the tracing. ECGs will be interpreted by a qualified physician (the investigator or qualified designee) at the clinical study site.

Refer to Section [6.1](#) for reporting AEs.

5.2.4 Vital signs

Vital sign measurements in this study will include sitting systolic and diastolic BP and pulse. Vital signs should be measured after the patient rests for approximately 5 minutes and with the patient in a sitting position.

BP measurement with a properly calibrated and validated instrument should be used. Patients should be seated quietly for at least 5 minutes in a chair rather than on an examination table, with feet on the floor and arm supported at heart level. An appropriate-sized cuff (cuff bladder encircling at least 80% of the arm) should be used to ensure accuracy. There will be 2 BP measurements made at least 30 seconds apart. Both BP measurements as well as the calculated average will be entered in the eCRF. The same arm should be used for all BP measurements during the study.

BP and pulse measurement must be performed in the seated position.

5.2.5 Other safety assessments

5.2.5.1 Cardiovascular events

Deaths (including cause of death [cardiovascular related vs. noncardiovascular]) and cardiovascular events (including myocardial infarction, stroke, acute coronary syndrome, ventricular fibrillation/tachycardia, and congestive heart failure requiring hospitalization) considered to be SAEs should be reported to the safety data entry site within 24 hours (refer to Section 6.4).

5.2.5.2 Pancreatitis

All SAEs of pancreatitis should be reported to the safety data entry site within 24 hours (refer to Section 6.4).

5.2.5.3 Liver function test abnormalities

Please see Appendix C, 'Algorithm on Management of Sustained Elevated Liver Safety Abnormalities', for further guidance. Investigators should contact the medical monitor if a patient develops a liver function test abnormality.

5.2.5.4 Injection-site adverse events

Small, asymptomatic, SC nodule formation at the injection site is an expected event associated with sustained release delivery systems.

Injection sites should be routinely examined at each study site visit. If any injection-site reaction meets the criteria for an AE (refer to Section 6.1), the event is to be reported on the AE eCRF, with the reaction described as specifically as possible. In the rare event of a severe injection site-related AE, the affected patient may be asked to undergo further evaluation which could include a biopsy of the injection site or nodule, if appropriate.

